5.4.3 Translational Tumor Immunology Program (TTIP) Laboratory, [REDACTED]

All samples are physically stored in [REDACTED] in secure, limited-access facilities with sufficient security, backup, and emergency support capability and monitoring to ensure long-term integrity of the specimens for research. Samples are logged, barcoded and tracked using Freezerworks Summit. This data storage software allows secure tracking of specimens that are completely de-identified, coded linked and tracked with barcodes only. Freezerworks has the capacity to fully audit all individual specimen processes such as location, aliquoting, thawing and shipping. Acquired samples are immediately transported to the NIDCD tissue core where

they are processed and barcoded. The participant sticker that was used for transport is immediately destroyed. Unique barcodes generated for each individual sample are linked to participant identification numbers given to laboratory staff by NIDCD research nurses. These unique participant numbers correspond to participant information that is stored in CTDM. Protected participant information in CTDM will be recorded by NIDCD Research Nurses. Aside from the participant label that is immediately destroyed after specimen transport, laboratory staff will not have access to protected participant information.

Investigators are granted view, input, and withdrawal authority only for their specimens. They may not view specimen data or access specimens for which they have not been authorized. Access to specimen storage is confined to repository staff. Visitors to the repositories are escorted by repository staff at all times

Tissue biopsies will be ordered in CRIS and any linked protected participant data will be stored in the Clinical Trial Data Management (CTDM) system. Should a CRIS screen not be available, the CRIS downtime procedures will be followed. All tissue biopsies collected will be coded and stored in the NIDCD Biospecimen Tissue Bank.

5.4.4 Procedures for Storage of Tissue Specimens in the Laboratory of Pathology

Tissues designated for clinical diagnostics are transported to the Laboratory of Pathology (LP) where they are examined grossly, and relevant portions are fixed, embedded in paraffin and sectioned and stained for diagnostic interpretation. Unutilized excess tissue that is not embedded in paraffin is stored in formalin for up to three months, in accordance with College of American Pathologists/Joint Commission on Accreditation of Healthcare Organizations (CAP/JCAHO) guidelines, and then discarded. Following completion of the diagnostic workup, the slides and tissue blocks are stored indefinitely in the LP's clinical archives. All specimens are catalogued and retrieved utilizing the clinical laboratory information systems, in accordance with CAP/JCAHO regulations. The use of any stored specimens for research purposes is only allowed when the appropriate IRB approval has been obtained. In some cases, this approval has been obtained via the original protocol on which the participant was enrolled.

5.4.5.2 Sample Processing

Samples will be processed immediately upon receipt by the ██████████. Biospecimens will be collected and processed using validated SOPs that will ensure both specimen quality and

participant confidentiality. Using a computerized inventory system and a backup hardcopy process, all specimen collection and processing steps will be documented, and the specific location of each specimen will be tracked. Each new specimen collected will be assigned a unique barcode identifier that can be linked to the original specimen collected and other relevant information within the inventory system. Specimen labels will indicate protocol number, order in which the participant enrolled on the trial, type of sample, as appropriate. The inventory process contains other security provisions sufficient to safeguard participant privacy and confidentiality. Access to the inventory system and associated documents is restricted to appropriate individuals. Requests to use specimens stored in the repository must be approved by the trial Principal Investigator. SOPs ensure that any changes in informed consent made by a participant and relayed to the trial Principal Investigator will be reflected in the inventory system to ensure that specimens are destroyed as appropriate. All laboratory personnel are trained to adhere to SOPs and are monitored for high-quality performance. Samples are stored in labeled boxes in secured freezers (i.e., -80°C, liquid nitrogen or other, as appropriate) according to stability requirements. These freezers are located in the [REDACTED]

5.4.6 Protocol Completion/Sample Destruction

All specimens obtained in the protocol are used as defined in the protocol. Any specimens that are remaining at the completion of the protocol will be stored in the conditions described in sections above. The study will remain open so long as sample or data analysis continues. Samples from consenting subjects will be stored until they are no longer of scientific value or if a subject withdraws consent for their continued use, at which time they will be destroyed.

The PI will record any loss or unanticipated destruction of samples as a deviation. Reports will be per the requirements of section [7.2](#).

If the participant withdraws consent the participant's data will be excluded from future distributions, but data that have already been distributed for approved research use will not be able to be retrieved.

6 DATA COLLECTION AND EVALUATION

6.1 DATA COLLECTION

The PI will be responsible for overseeing entry of data into a 21 CFR Part 11-compliant data capture system provided by the NCI CCR and ensuring data accuracy, consistency and timeliness. The principal investigator, associate investigators/research nurses and/or a contracted data manager will assist with the data management efforts. Primary and final analyzed data will have identifiers so that research data can be attributed to an individual human subject participant.

All adverse events, including clinically significant abnormal findings on laboratory evaluations, regardless of severity, will be followed until return to baseline or stabilization of event.

Document AEs from the administration of the first study intervention through 30 after the study agent (s) was/were last administered. Beyond 30 days after the last intervention, only adverse events which are serious and related to the study intervention need to be recorded.

An abnormal laboratory value will be recorded in the database as an AE only if the laboratory abnormality is characterized by any of the following:

- Results in discontinuation from the study

- Is associated with clinical signs or symptoms
- Requires treatment or any other therapeutic intervention
- Is associated with death or another serious adverse event, including hospitalization.
- Is judged by the Investigator to be of significant clinical impact

If any abnormal laboratory result is considered clinically significant, the investigator will provide details about the action taken with respect to the test drug and about the participant's outcome.

Adverse Events of grade 1 will not be collected.

End of study procedures: Data will be stored according to HHS, FDA regulations and NIH Intramural Records Retention Schedule as applicable.

Loss or destruction of data: Should we become aware that a major breech in our plan to protect subject confidentiality and trial data has occurred, his will be reported expeditiously per requirements in section [7.2.1](#)

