3.1.1 Dose Limiting Toxicity

Dose-limiting toxicity (DLT) will be defined as any one of the following adverse events (AEs), as defined by CTCAE v5.0, possibly attributable to study drugs by the Investigator, that occur within 28 days after the start of study therapy:

- Any Grade 4 AEs, except for:
 - laboratory values that are determined to not be clinically significant or single laboratory valued that resolve to Grade ≤ 1 or baseline grade within 7 days with adequate medical management.
 - adverse drug reaction which in the opinion of the investigator is not clinically relevant or can be medically managed with minimal risk to the participant (e.g. placement of a pleural catheter for recurrent inflammatory pleural effusions)
- Average QTcf ≥ 501 msec or > 60 msec change from baseline (Grade 3)
- Any Grade 3 AEs except for any of the following:
 - Grade 3 flu-like symptoms or fever, as well as associated symptoms of fatigue, headaches, nausea, emesis which can be controlled with conservative medical management.
 - Tumor flare phenomenon defined as local pain, irritation, or rash localized at sites of known or suspected tumor.

- Any Grade ≥ 3 drug-related amylase or lipase abnormality that is not associated with symptoms or clinical manifestations of pancreatitis.
- Grade 3 Hgb decrease (< 8.0 g/dL) that is clinically manageable with blood transfusions or erythroid growth factor use does not require treatment discontinuation.
- Keratoacanthoma and squamous cell carcinoma of the skin.
- Any endocrinopathy that can be medically managed with hormone replacement
- Grade 3 neutropenia without fever
- Since the safety profile of M7824 is well characterized (see IB), a single grade 3 adverse event known to be associated with M7824, as per IB section 6.2.6 will not be considered a DLT.
 - Additionally, M7824 has a known potential to cause bleeding, with a rate of grade 3 bleeding events as high as 15.3% [92]. Therefore a grade 3 bleeding event will not be considered a DLT.
- Any grade 3 adverse drug reaction which in the opinion of the investigator is not clinically relevant or can be medically managed with minimal risk to the participant (e.g. placement of a pleural catheter for recurrent inflammatory pleural effusions)
- Any grade 3 or higher adverse event or unexpected toxicities due to the combination of therapies that would not be expected with individual agents alone, will be considered a DLT.

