3.4.2 SX-682

If any SX-682 related AE observed is grade > 2 (except for electrolyte abnormalities that can be easily replenished or other lab abnormalities that have no clinical consequence or can be easily medically managed with minimal risk to the participant), treatment should be delayed by 1 week (except for hyperbilirubinemia where drug will be held for grade 2) – and up to 4 consecutive weeks. If, with a delay of up to 4 weeks, the treatment related AE resolves, then SX-682 can be resumed at the same dose level or at a lower dose level per the PI discretion.

If, after 4 weeks of delay, all treatment related AEs have still not resolved (to grade ≤ 1), then any further treatment with SX-682 should be delayed until AEs are resolved (to grade ≤ 1), and then reduced by one dose level at the time of reinitiating.

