10.4.2 Analysis of the Primary Endpoints

The toxicity grades per participant will be tabulated and reported by dose level during dose escalation (Arms 1 and 2). This will also include separate evaluations for the initial monotherapy evaluations preceding the evaluation of the combination at each dose level.

In Arm 3, the fraction of participants who experience a response in each disease-specific cohort will be reported along with 95% two-sided confidence intervals.

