10.4.5 Safety Analyses

The fraction of participants who experience a toxicity, by grade and type of toxicity, will be tabulated per dose level (both single agent and combination of agents) during the Arms 1 and 2 portion of the trial. Participants who take one dose or more of SX-682 will be evaluable for safety.

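### Asymptomatic graded laboratory toxicities may be missing from the Arms 1 and 2 by-grade toxicity tables, because Section 6.1 filters laboratory AEs and Section 10.4 plans no table from measured values

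*Combined protocol and SAP*

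**What the plan says.** Section 6.1 sets the recording rule: "An abnormal laboratory value will be recorded in the database as an AE only if the laboratory abnormality is characterized by any of" five listed features. Three of them matter here: "Results in discontinuation from the study", "Requires treatment or any other therapeutic intervention" and "Is judged by the Investigator to be of significant clinical impact". The other two are an association with signs or symptoms, and an association with death or another serious event.

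Section 10.4.2 gives the primary analysis for dose escalation: "The toxicity grades per participant will be tabulated and reported by dose level during dose escalation (Arms 1 and 2"), with the monotherapy lead-in evaluated separately. Section 10.4.5 adds "The fraction of participants who experience a toxicity, by grade and type of toxicity", per dose level. Neither section names its data source or mentions a table derived from measured laboratory values.

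Other sections name or act on laboratory grades directly. Section 3.1.1 lists "Grade 3 neutropenia without fever", and grade 3 or higher amylase or lipase without signs of pancreatitis, among the exceptions to the DLT definition. Section 3.4.2 delays SX-682 for related AEs above grade 2, with the qualification "except for hyperbilirubinemia where drug will be held for grade 2". Section 3.4.4.1 requires M7824 to be stopped permanently if an isolated, asymptomatic grade 3 or higher liver-test, amylase or lipase abnormality has not resolved to grade 1 or below within 56 days.

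**The concern.** A hold, a dose reduction or the permanent stop of a single drug is not a reason to record a laboratory AE under 6.1. The listed criterion is leaving the study, and the protocol treats that separately from stopping therapy (3.7.2 against 3.7.1). It also lets a participant continue on the remaining drugs after one is stopped (3.1.2, 3.4.1). So a laboratory abnormality can change a participant's treatment without meeting any 6.1 criterion except the investigator's view of its clinical impact, for which the protocol gives no definition.

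The toxicity tables are the planned place to see toxicity that is not dose-limiting. Single-agent SX-682 safety is an Arm 1 primary objective, and in both arms the objective becomes a description of safety and tolerability if no MTD is reached (1.1.1). Events exempt from the DLT definition do not enter the 3+3 count. If 6.1 also keeps them off the AE form, they may appear in no planned analysis. Whether they do can differ between participants with the same laboratory value, which weakens comparison across dose levels of three to six people.

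**Working it through.** The documents give no figure to reproduce and no rate of asymptomatic laboratory toxicity. The check is therefore a comparison of rules, followed by an illustration of scale.

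**Step 1. Rules side by side.** Take each abnormality as asymptomatic, untreated and not linked to a serious event.

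| Abnormality | Where the protocol names it | Must 6.1 record it? |
|---|---|---|
| Grade 3 neutropenia without fever | 3.1.1, exempt from DLT | No; only if judged of significant impact |
| Isolated grade 3 or higher amylase or lipase | 3.1.1, exempt from DLT; 3.4.4.1, exempt from temporary stop but subject to the 56-day limit | No; stopping M7824 alone is not leaving the study |
| Grade 2 bilirubin | 3.4.2, SX-682 held | No; a hold is not listed |
| Isolated grade 3 or higher transaminase, alkaline phosphatase or bilirubin unresolved at 56 days | 3.4.4.1, M7824 stopped permanently | No; same reason |

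In every row, recording depends on the investigator-judgement criterion.

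**Step 2. Could an actual DLT be lost?** Section 3.1.1 exempts grade 4 laboratory values judged not clinically significant, and grade 3 reactions judged not clinically relevant or manageable with minimal risk. A laboratory value that remains a DLT is one the investigator has not excused on those grounds, so it should also meet the 6.1 impact criterion. Section 3.1.2 separately requires every DLT to be documented. No loss of a DLT follows from the text.

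**Step 3. Which measured values exist?** The study calendar (3.5) schedules CBC and biochemistry at screening, at baseline and on Days 1 and 15 of each cycle. Amylase and lipase are drawn at screening and baseline and then every 8 weeks (footnote 11). The lead-in column shows no safety laboratory draw, so laboratory grades for the monotherapy period would rest on the Cycle 1 Day 1 sample.

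**Step 4. Illustration of scale.** Assume one event at a dose level goes unrecorded. The bounds below are one-sided 95% Clopper-Pearson upper limits. They are added here; the plan specifies no interval for toxicity fractions.

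- Six participants, event recorded: 1/6 = 16.7%. The bound solves (1−p)^6 + 6p(1−p)^5 = 0.05, giving p = 58.2%.
- Six participants, event missed: 0/6 = 0%. The bound is 1 − 0.05^(1/6) = 39.3%.
- Three participants: 1/3 = 33.3% becomes 0/3 = 0%.

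This shows what one missed event does to a reported fraction. It does not say how often 6.1 would cause one.

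**The case against.** The strongest reply is that 6.1 is less restrictive than it looks. It admits asymptomatic values that are treated or judged significant, and it asks for the action taken with the drug whenever a laboratory result is considered clinically significant. Section 3.4.2 also exempts laboratory abnormalities without clinical consequence, and it is worded for an SX-682-related AE, so a bilirubin rise that triggers the hold is arguably an AE already. Sections 10.4.2 and 10.4.5 do not confine the tables to AE-form entries, and the DSMB reviews clinical laboratory data (7.5.2).

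Much of this stands, and it is why the tables may omit events rather than must. It does not close the gap. The link in 6.1 runs from clinical significance to drug action; nothing makes a drug action a reason to record. If 3.4.2 treats the bilirubin rise as an AE while 6.1 need not enter it as one, the two sections need reconciling. DSMB review of laboratory data is not a planned trial analysis.

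A reader might infer more than the documents support:

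- **That 6.1 hides DLTs or distorts escalation.** The neutropenia and amylase/lipase examples are exceptions to the DLT rule, and DLTs are documented separately.
- **That the RP2D rests on these tables.** Section 3.1.4 allows the RP2D to differ from the MTD but does not name the tables as its basis; 3.1.5 ties the RP2D to completion of the DLT period by the sixth participant.
- **That laboratory toxicity is under-counted at every dose level.** No event rate is given, so this cannot be stated as fact.
- **That 6.1 contradicts the AE definition in 8.1.1.** That section is a general definition; 6.1 is the recording rule.

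**Conclusion.** The concern holds as a risk of incomplete and judgement-dependent reporting in the Arms 1 and 2 toxicity tables. It covers asymptomatic graded laboratory values, including some that lead to a hold or permanent stop of one drug. It assumes that the tables are built from recorded AEs, which the plan neither says nor excludes, and that 6.1 is followed as written. The number of events affected cannot be estimated from the documents. At three to six participants per level, each one moves a reported fraction by 17 to 33 percentage points. The 3+3 decisions and the Arm 3 response analysis are not affected. The point should be acted on because the data are already collected and the remedy removes the dependence on judgement.

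**What to change.** 1. In 10.4.2 and 10.4.5, add tables of the worst post-baseline CTCAE v5 laboratory grade and the shift from baseline, by arm and dose level. Derive them from all scheduled CBC and biochemistry values (Days 1 and 15) and the 8-weekly amylase and lipase values. Use the Cycle 1 Day 1 predose draw, where available, as the lead-in assessment.
2. Reconcile 6.1 with 3.4 by recording as an AE any laboratory abnormality that leads to a hold, reduction, skipped dose or stop of any study drug.

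The cost is some programming, one line in 6.1 and a little extra data entry. No new samples are needed and no clinical rule changes. The drawback is that reported laboratory toxicity rates may look slightly higher than under the current wording.

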6.2 DATA SHARING PLANS

6.2.1 Human Data Sharing Plan

The PI will share coded linked human data generated in this research for future research

- in a NIH-funded or approved public repository clinicaltrials.gov and dbGaP
- in BTRIS
- in publication and/or public presentations
- with approved outside collaborators under appropriate agreements
- at the time of publication or shortly thereafter.

6.2.2 Genomic Data Sharing Plan

Unlinked genomic data will be deposited in public genomic databases such as dbGaP in compliance with the NIH Genomic Data Sharing Policy.

6.3 RESPONSE CRITERIA

For the purposes of this study, participants should be re-evaluated for response according to schedule in the Study Calendar, section [3.5](#).

In the event of a PR or CR tumor imaging assessments may be performed every 3 months (+/- 2 weeks) at the discretion of the investigator. In addition to a baseline scan, confirmatory scans can also be obtained 4 to 8 weeks following initial documentation of objective response per the discretion of the primary investigator.

The preferred method of disease assessment is CT with contrast. If CT with contrast is contraindicated, CT of the chest without contrast and MRI scan of the abdomen/pelvis is preferred. Additional assessment of tumor response may include the following evaluations; nuclear bone scan for subjects with known/suspected bone lesions; and CT or MRI scan of the brain (only as clinically warranted based on symptoms/findings).

Brain CT / MRI scan should be performed, if clinically indicated by development of new specific symptoms or on the discretion of the Primary Investigator. For each subject, the Investigator will

designate 1 or more of the following measures of tumor status to follow for determining response: CT or MRI images of primary and / or metastatic tumor masses, physical examination findings, and the results of other assessments. All available images collected during the trial period will be considered. The most appropriate measures to evaluate the tumor status of a subject should be used. The measure(s) to be chosen for sequential evaluation during the trial have to correspond to the measures used to document the progressive tumor status that qualifies the subject for enrollment.

Progressive disease should be confirmed by imaging 4 to 8 weeks (preferably at 4 weeks, but not more than 8 weeks) after progression has been diagnosed according to RECIST 1.1. before the participant is removed from treatment [93]. If progression is based on the occurrence of a new lesion in an area not scanned at Baseline, a further on-study scan 4 to 8 weeks later should be considered before performing the 28-Day Safety Follow-up visit.

Tumor responses to treatment will be assigned based on the evaluation of the response of target, non-target, and new lesions according to RECIST 1.1 (all measurements should be recorded in metric notation).

To assess objective response, the tumor burden at baseline will be estimated and used for comparison with subsequent measurements. At baseline, tumor lesions will be categorized in target and non-target lesions according to RECIST 1.1.

Results for these evaluations will be recorded with as much specificity as possible so that pre and post-treatment results will provide the best opportunity for evaluating tumor response.

The Investigator may perform scans in addition to a scheduled trial scan for medical reasons or if the Investigator suspects PD.

iRECIST will also be used for exploratory endpoints (See section [6.3.3](#))

For the primary endpoint antitumor activity will be evaluated with target and/or non-target lesions according to Response Evaluation Criteria in Solid Tumors (RECIST) Version 1.1. [93].

Palliative radiotherapy delivered in a normal organ-sparing technique may be administered during this trial. The assessment of PD will not be based on the necessity for palliative radiotherapy.

If a target lesion is radiated during the course of treatment, this target lesion will no longer be considered a measurable lesion and will be removed from the target lesion sum moving forward as is recommended in RECISTv1.1.

